6.6 Safety Assessments

6.6.1 Unanticipated Problems

Unanticipated problems (UAPs) include, in general, any incident, experience, or outcome that meets the following criteria:

unexpected in terms of nature, severity, or frequency given (a) the research procedures that are
described in the protocol-related documents, such as the IRB-approved research protocol and
informed consent document; and (b) the characteristics of the participant population being
studied;

UAPs are considered to pose risk to participants or others when they suggest that the research places participants or others at a greater risk of harm (including physical, psychological, economic, or social harm) than was previously known or recognized.

6.6.2 Adverse Events

An adverse event is any untoward or unfavorable medical occurrence in a human participant, including any abnormal sign (for example, abnormal physical exam or laboratory finding), symptom, or disease, temporally associated with the participant's participation in the research, whether or not considered related to the participant's participation in the research.

6.6.3 Serious Adverse Events

A serious adverse event (SAE) is one that meets one or more of the following criteria:

- Results in death
- Is life-threatening (places the participant at immediate risk of death from the event as it occurred)
- Is disabling or incapacitating
- Results in inpatient hospitalization or prolongation of existing hospitalization
- Results in a persistent or significant disability or incapacity
- Results in a congenital anomaly or birth defect
- An important medical event that may not result in death, be life threatening, or require
 hospitalization may be considered an SAE when, based upon appropriate medical judgment, the
 event may jeopardize the participant or may require intervention to prevent one of the outcomes
 listed in this definition.

6.6.4 Safety Assessment and Follow-Up

At each study visit, the investigator (or designee) will inquire about the occurrence of AE/SAEs since the last visit. Events will be followed for outcome information until resolution or stabilization.

The subjects who receive ultrasound contrast agent will be monitored for AEs during the entire procedure. All AEs, including observed or volunteered problems, complaints, signs or symptoms, and diagnoses, occurring from the initiation of Optison dosing until 30 minutes from the completion of the Optison administration will be recorded on a serious or non-serious AE data form, whether or not associated with the use of the trial medication.

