The primary measure of tumor response will be evaluated using mRECIST criteria as determined by Drs. [name] and [name] in consensus using the patients clinically scheduled 3-4 month contrast enhanced MRI or CT. As a secondary measure of tumor response, changes in alpha fetal protein (AFP; collected as blood samples at approximately one month post embolization as standard of care) will be recorded when clinically available. Tumoral perfusion for each imaging plane will also be calculated as the slope of contrast reperfusion based on change in signal intensity over time. Perfusion values for each plane will then be averaged over the entire mass and normalized to values immediately post treatment (day 1). Finally, each patient's progression free survival and overall survival will be monitored, although this is a tertiary outcome for this study and many patients are expected to surpass the timeline of this pilot study. Safety outcomes will be determined using changes in vital signs, observed and self-reported adverse events, and changes in liver function tests (LFTs) at approximately 1 month post-embolization when available (preformed as part of clinical standard of care). Liver function tests (LFTs) include blood tests for alanine aminotransferase, alkaline phosphatase, asparate aminotransferase, bilirubin, albumin, total protein, and prothrombin time. SPECT imaging will be evaluated for all available cases by two blinded radiologists to evaluate if the initial UTMD session skews Therasphere distribution in the liver.

The proposed agent for the current study, Optison™ is a sterile non-pyrogenic suspension of encapsulated perflutren microbubbles [Goldberg et al 2001; Miller & Nanda 2004]. The contrast agent is consists of a human serum albumin shell with perflutren core and contains 5.0 - 8.0 x 10⁸ microspheres/ ml. The microbubble agent is supplied in a standard-size 3 ml vial and is prepared by manually shaking the vial. Optison will be stored in a secure refrigerator, with only the study investigators and research personnel having access. Optison is currently only approved for use in echocardiography. The agent will be used as an off-label indication for this study, but within approved dosage recommendations.

Statistical Methodology: This project is a pilot study to determine if microbubble destruction and reperfusion can used to improve treatment response of HCC to radioembolization and predict early treatment response.

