3. TRIAL DESIGN

This is an open-label, randomized trial that will be conducted at one clinical site to determine if ultrasound-triggered microbubble destruction (UTMD) can be used to improve radioembolization of HCC. The subject population will be patients scheduled for radioembolization of a previously untreated HCC mass at Thomas Jefferson University. All patients will undergo single-photon emission computed tomography (SPECT) imaging as part of their standard of care to confirm effective localization of the Y90 beads. For research purposes, imaging of the chest will be performed when possible to assess extrahepatic distribution of Y90 using a planar imaging acquisition. Patients will be randomly assigned to either the experimental (UTMD + radioembolization) or control group (radioembolization alone) by the research coordinator using a random assignment generator. For patients assigned to the experimental group, the study will consist of up to three contrast-enhanced ultrasound (CEUS) exams: 1-6 hours post radioembolization, and approximately 7 and 14 days post treatment. Treatment response will be evaluated using modified response evaluation criteria in solid tumors (mRECIST) at 1 and 4 months post treatment based on the patient's clinically scheduled

contrast-enhanced MRI or CT. For patients assigned to the control group, only outcomes data will be collected (without intervention).

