6.4 Safety Monitoring

Adverse events in patients receiving ultrasound contrast agents will be monitored during the entire procedure and for 30 minutes from the completion of Optison infusion. Specifically, the patient will be monitored with non-leading questions to monitor the patient for the transient side effects that are described below. Changes in liver function tests (preformed clinically prior to radioembolization and 1 month) will be recorded and compared to the control group to evaluate safety and liver toxicity.

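### Section 6.6.4 gives two unreconciled adverse-event collection rules, and no adverse-event ascertainment is specified for controls or after about day 14

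*Combined protocol and SAP*

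**What the plan says.** Section 6.6.4 has two paragraphs. The first reads "At each study visit, the investigator (or designee) will inquire about the occurrence of AE/SAEs since the last visit", and adds "Events will be followed for outcome information until resolution or stabilization". The second concerns patients given contrast, and says that events "occurring from the initiation of Optison dosing until 30 minutes from the completion of the Optison administration will be recorded" on a serious or non-serious form. Section 6.4 sets the same limit for monitoring: adverse events in contrast recipients "will be monitored during the entire procedure and for 30 minutes from the completion of Optison infusion".

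Section 6.6.5 refers to Appendix C for the period over which events must be documented. The appendix table is broken in the text available. What can be read there is reporting deadlines by grade, expectedness and relatedness. No collection period is visible.

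On the control arm, section 3 states "For patients assigned to the control group, only outcomes data will be collected (without intervention". Section 3.1 asks nothing further of controls and has the coordinator obtain their laboratory, imaging and outcome data from routine care. Section 6.7 counts a control as complete on consent to share liver function, imaging and outcomes. None of these places names adverse events.

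The synopsis and sections 3 and 6.5 list adverse events among the safety outcomes, without naming an arm. Section 6.4 says that changes in liver function tests from before radioembolization to 1 month "will be recorded and compared to the control group to evaluate safety and liver toxicity". The synopsis describes this outcome as "changes in liver function tests (LFTs) at approximately 1 month post-embolization when available".

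**The concern.** The infusion-plus-30-minutes window suits acute reactions to a contrast agent. The hypothesis in sections 1 and 1.2 is different: cavitation is meant to sensitise the tumour to Y-90 radiation that goes on being delivered for days. A harm from that interaction need not show itself within half an hour of an infusion.

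Staff are told to ask about events between visits, but the only explicit instruction on what goes on the form covers the short window. Two coordinators could follow the same section and produce different adverse-event data. Whatever is collected in the experimental arm also has no specified counterpart among controls, so a randomised trial would report one of its stated safety outcomes for one arm only. A report of no added toxicity could then reflect what was not collected.

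**Working it through.** The plan gives no adverse-event rate, target or power figure, so there is nothing to reproduce. The check is what each rule would cover.

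**Inputs.** Infusion of 5 ml Optison in 50 ml saline at 120 ml/hour (sections 5.1 and 6.3), so 50 to 55 ml in total depending on whether the agent adds to the volume. Observation of 30 minutes (6.4, 6.6.4). Up to three exams, at 1-6 hours and about days 7 and 14, of which one of the later two may be missed (3.1). Y-90 half-life of 64 hours (1.1).

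**Narrow rule: form recording in the window.**
- Infusion time: 50/120 h = 25 min; 55/120 h = 27.5 min.
- Window per exam: 55 to 57.5 min.
- Three exams: 165 to 172.5 min = 2.75 to 2.9 h.
- Share of 14 days (336 h): 2.75/336 = 0.82%; 2.875/336 = 0.86%.
- With one later exam missed: 110 to 115 min = 1.8 to 1.9 h, or about 0.55 to 0.57%.
- Section 6.7 counts four exams for completion, against three elsewhere. Four would give 220 to 230 min = 3.7 to 3.8 h, or about 1.1%.

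**Radiation delivered in those windows.** The fraction decayed by time t is 1 − 0.5^(t/64).
- By day 7: 1 − 0.5^(168/64) = 84%. By day 14: 1 − 0.5^(336/64) = 97%.
- Inside three 57.5-minute windows starting at 1 to 6 h, 168 h and 336 h: the sum of 0.5^(a/64) − 0.5^((a+0.958)/64) over the three start times a is about 1.2%.

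**Wide rule: enquiry since the last visit.** Scheduled enquiry runs to about day 14, or to about day 7 if the last visit is the one missed. Taking a month as 30 days, 30 − 14 = 16 days then pass before the 1-month assessment with no scheduled enquiry.

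**Side by side.**

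| | Experimental | Control |
|---|---|---|
| Narrow rule | 2.75-2.9 h in 14 days | none specified |
| Wide rule | to about day 14 | none specified |
| Liver function tests | before treatment and about 1 month | same |

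Section 7.2.1 plans tests for liver function, SPECT reads, planar imaging and time to next treatment, among others. It names no adverse-event comparison.

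**The case against.** A reader might infer that adverse events are recorded only in the short window and not at all in controls, so that delayed toxicity can be neither seen nor compared. The documents do not support that.

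- **The wider reading is open.** The visit enquiry opens section 6.6.4, and the second paragraph can be read as an added window for acute reactions. Section 6.6.2 defines an adverse event by its timing relative to participation, with no 30-minute limit. Section 6.6.6 requires reporting of grade 3 to 5 events, and quarterly submission of all adverse-event and toxicity data, again with no such limit. Appendix C may hold a period that cannot be read here.
- **Liver toxicity can be compared in part.** Liver function tests are compared with control, and section 6.6.2 counts abnormal laboratory findings as adverse events. SPECT is read by two blinded radiologists, and progression and survival are followed in every patient. The condition about availability is attached to liver function tests in the synopsis, but not in sections 3, 6.4 or 6.5.
- **Exclusion of control events is an inference.** It comes from lists that do not mention them; no sentence forbids their collection.
- **No time course of toxicity is given.** That harms would appear over days to weeks is plausible from the half-life but is not stated.

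All of this stands against the stronger reading. It leaves three gaps. Reporting duties apply to events already known and do not say how they are to be found. Liver function tests at one post-treatment time would not show pain, fever, admission to hospital or an abnormality that had resolved. The SPECT reads address bead distribution, and progression and survival are tertiary outcomes.

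**Conclusion.** The point holds as a contradiction between two collection rules together with a gap in ascertainment. If the narrow rule governs, recording covers 0.8 to 0.9% of the first 14 days, assuming three full infusions at the stated rate. If the wide rule governs, the experimental arm is covered to about day 14. Under both, nothing is specified for controls or after about day 14, so adverse events as a stated outcome have no planned between-arm comparison. Comparison of liver function at about 1 month remains, so it would be wrong to say that delayed toxicity is invisible.

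The documents give no expected event rate, so no probability of missing an event is offered. The conclusion assumes that Appendix C contains no collection period; if it does, sections 6.4 and 6.6.4 still need to agree with it, and control ascertainment still needs to be stated. The primary efficacy analysis is unaffected, but the change should be made because it decides what the trial can say about safety.

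**What to change.** - Reconcile the two paragraphs of section 6.6.4, and align sections 6.4 and 6.6.5 with the result. State one collection period for both arms, from radioembolization to the standard-of-care assessment at about 1 month.
- For the by-arm comparison, use one method in both arms: chart abstraction by the coordinator from routine-care records, with CTCAE grade tabulated by randomised arm. Answers to questions put at the ultrasound visits should stay out of this table. The trial is open-label and only one arm is asked, so including them would tend to inflate the experimental arm's count.
- Report events solicited at those visits, and acute reactions up to 30 minutes after infusion, in separate tables for the experimental arm alone.
- Make sure that the control-arm consent described in section 6.7 covers adverse-event data, which it does not name at present.

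The cost is protocol wording, possibly consent wording, and extra abstraction by a coordinator who already obtains laboratory, imaging and outcome data for controls. Chart-based events may be incomplete in both arms, and the report should say so.

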6.6.5 Recording Adverse Events

The following subsections detail what information must be documented for each adverse event occurring during the time period specified in Appendix C: SKCC DSMP's AE/SAE Reporting Requirements.

Relationship to Study Intervention

The relationship to study intervention or study participation must be assessed and documented for all adverse events. Evaluation of relatedness must consider etiologies such as natural history of the

underlying disease, concurrent illness, concomitant therapy, study-related procedures, accidents, and other external factors.

The following guidelines are used to assess relationship of an event to study intervention:

Relationship

- 1. Related (Possible, Probable, Definite)
 - a. The event is known to occur with the study intervention.
 - b. There is a temporal relationship between the intervention and event onset.
 - c. The event abates when the intervention is discontinued.
 - d. The event reappears upon a re-challenge with the intervention.
- 2. Not Related (Unlikely, Not Related)
 - a. There is no temporal relationship between the intervention and event onset.
 - b. An alternate etiology has been established.

Expectedness

The PI is responsible for determining whether an AE is expected or unexpected. An AE will be considered unexpected if the nature, severity, or frequency of the event is not consistent with the risk information previously described for the intervention. Risk information to assess expectedness can be obtained from preclinical studies, the investigator's brochure, published medical literature, the protocol, or the informed consent document.

Severity of Event

Adverse events will be graded for severity according to the Common Terminology Criteria for Adverse Events (CTCAE) version 4.0

Intervention

Any intervention implemented to treat the adverse event must be documented for all adverse events.

6.6.6 Safety Reporting

Reporting to the IRB

Unanticipated Problems

All incidents or events that meet criteria for unanticipated problems (UAPs) as defined in Appendix C: SKCC DSMP's AE/SAE Reporting Requirements require the creation and completion of an unanticipated problem report form (OHR-20).

UAPs that pose risk to participants or others, and that are not AEs, will be submitted to the IRB on an OHR-20 form via the eazUP system within 5 working days of the investigator becoming aware of the event.

UAPs that do not pose risk to participants or others will be submitted to the IRB at the next continuing review.

Adverse Events

Grade 1 AEs will be reported to the IRB at continuing review.

Grade 2 AEs will be reported to the IRB at the time of continuing review.

Serious Adverse Events

SAEs will be reported to the IRB on OHR-10 forms via the electronic reporting system (eSAEy) according to the required time frames described below.

Grade 3-4 AEs that are unexpected and deemed to be at least possibly related to the study will be reported to the IRB within 2 working days of knowledge of the event.

Grade 3-4 AEs that are deemed unrelated to the study will be reported to the IRB within 5 working days.

Grade 5 AEs will be reported to the IRB within one working day of knowledge of the event.

All SAEs will be submitted to the IRB at continuing review, including those that were reported previously.

Reporting to the Sidney Kimmel Cancer Center DSMB

On a quarterly basis, all AEs and SAEs, safety and toxicity data, and any corrective actions will be submitted to the DSMC per the DSMP. The quarterly report to DSMC will also include any unanticipated problems that in the opinion of the PI should be reported to the DSMC.

For expedited reporting requirements, see DSMC AE/SAE Reporting Requirements.

FDA Reporting

The investigator is required to submit all unexpected and serious adverse events to the FDA within 48 hours. Fatal adverse events related to treatment which are unexpected must be reported within 24 hours. Fatalities not related to the study drug/device must be reported within 5 days.

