APPENDIX A - INVESTIGATOR OBLIGATIONS

A. Institutional Review Board (IRB) and Human Subjects Research Review Board (HSRRB) Review/Approval

The protocol and informed consent for this study must be reviewed and approved by an appropriate IRB and HSRRB prior to enrollment of participants in the study. It is the responsibility of the investigator to assure that all aspects of the ethical review are conducted in accordance with FDA Regulations 21 CFR Part 56. A letter documenting the IRB and HSRRB approval which specifically identifies the study/protocol must be obtained by the investigator prior to initiation of the study. Amendments to the protocol will be subject to the same requirements as the original protocol. The HSRRB must review and approve each modification to the study prior to implementation.

A progress report with a request for re-evaluation and re-approval will be submitted by the investigator to the IRB and HSRRB at intervals required by the IRB, and not less than annually.

After completion or termination of the study, the investigator will submit a final report to the IRB. This report should include: deviations from the protocol, the number and types of participants evaluated, the number of participants who discontinued (with reasons), results of the study, if known, and all AEs, including deaths.

B. Informed Consent

Signed, written informed consent which conforms to FDA Regulation 21 CFR Part 50, must be obtained from each participant prior to entering the study. Each participant will be provided a written consent form and verbal information in an understandable manner which describes the nature and duration of the study. The research study coordinator or the investigator will conduct the informed consent interview in a private examination room. The potential subject will be allowed to discuss the study with the investigator, research study coordinator, or any persons who may have accompanied the potential subject. Additionally, the participant must be allowed adequate time to consider the potential risks and benefits associated with his participation in the study. The research study coordinator will sign the informed consent as the person conducting the consent interview.

C. Data Reporting and Data Forms

Data reflecting participant's experiences with the study will be recorded on CRFs by the investigator.

D. Records Retention

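### A risk-posing unanticipated problem that is itself a non-serious Grade 1 or 2 adverse event has no expedited IRB deadline and waits for continuing review

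*Combined protocol and SAP*

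**What the plan says.** Section 6.6.1 defines a UAP broadly, as "any incident, experience, or outcome that meets the following" criteria. The criterion shown is unexpectedness. A UAP poses risk "when they suggest that the research places participants or others at a greater risk of harm" than was previously recognised. No severity grade is needed.

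Section 6.6.6 then sets the IRB deadlines:

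- UAPs that pose risk "to participants or others, and that are not AEs, will be submitted to the IRB on an OHR-20 form", to be sent "via the eazUP system within 5 working days of the investigator becoming aware of the event".
- UAPs that pose no risk wait for the next continuing review.
- For low-grade AEs: "Grade 1 AEs will be reported to the IRB at continuing review", and "Grade 2 AEs will be reported to the IRB at the time of continuing review".
- Deadlines of 1, 2 or 5 working days appear only under the serious adverse event heading, for Grades 3 to 5.

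Appendix A, part A, has progress reports and re-approval requests go to the IRB "at intervals required by the IRB, and not less than annually".

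**The concern.** The two sets of rules overlap, and the overlap takes the slower deadline. Section 6.6.2 defines an AE widely: any untoward occurrence in a participant, including an abnormal sign, whether or not it is thought related. An unexpected low-grade event in a participant can therefore be an AE and also a UAP that points to a new risk. The UAP sentence excludes it because it is an AE, and the AE lines then treat it as routine because of its grade. Neither Grade 1 nor Grade 2 has an exception for events that are unexpected, related or UAPs.

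What is at stake is when the IRB hears of a new risk while enrolment and UTMD sessions continue. The agent is used off-label, with cavitation starting 1 to 6 hours after Y-90 treatment. A signal that the investigator has already judged to indicate greater risk would go to the IRB on the timetable for problems that carry none.

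**Working it through.** The check has two steps: trace each type of event to its IRB deadline, then size the longest gap.

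**Step 1: deadlines by type of event (Section 6.6.6)**

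| Event | IRB deadline |
|---|---|
| UAP that poses risk, not an AE | 5 working days |
| UAP that poses risk and is a non-serious Grade 1 or 2 AE | continuing review |
| UAP that poses no risk | next continuing review |
| Grade 3-4 AE, unexpected and at least possibly related | 2 working days |
| Grade 3-4 AE, unrelated | 5 working days |
| Grade 5 AE | 1 working day |

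The second row follows because no sentence sets a deadline for a risk-posing UAP that is an AE, so the AE lines are the only ones left. It has the timing of the third row, not the first.

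Other routes that might close the gap:

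- **OHR-20 form.** It must be completed for every UAP, but that sentence gives no submission deadline.
- **Appendix C.** The legible Grade 1 and Grade 2 cells point to the quarterly DSMC meeting and IRB annual review. The cell that appears to cover unexpected Grade 2 events related to treatment is damaged in the text available here, so it cannot be relied on either way.
- **FDA rule.** It is most naturally read as covering events that are both unexpected and serious, plus fatalities.
- **DSMC report.** All AEs go in quarterly. UAPs are added when the PI thinks they should be.

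**Step 2: size of the gap**

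Inputs:

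- 52 patients per group (Section 7.2.1).
- Recruitment of 83 months as stated in Section 3.1. The dates given there, March 2017 to December 2023, count to 10 + 6 × 12 = 82 months.
- Up to 3 exams per UTMD patient (Sections 3 and 3.1). The completion criterion in Section 6.7 mentions four; three is used here because the design sections cap it there.
- Review at least once a year (Appendix A).

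Calculation:

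- UTMD patients per year: 52 / (83/12) = 7.5; 52 / (82/12) = 7.6.
- Sessions per year: 52 × 3 / (83/12) = 22.6; 52 × 3 / (82/12) = 22.8.
- Per quarter, until the DSMC report: about 7.5 / 4 = 1.9 patients and 22.6 / 4 to 22.8 / 4 = 5.6 to 5.7 sessions.

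The longest IRB delay is therefore about 12 months, with 7 to 8 further patients and about 23 sessions. The longest wait for the DSMC is about 3 months, with about 2 patients and 6 sessions.

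**The case against.** The best defence is that the exclusion of AEs was probably meant to avoid reporting the same event twice. That works for Grades 3 to 5, which have short deadlines of their own. It does not work for Grades 1 and 2, which have none.

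A reader might infer more than the text supports, in three ways.

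- **That a problem loses its 5-day deadline as soon as it causes a mild symptom.** The clause excludes UAPs that are AEs, not UAPs that lead to one. Because the definition covers incidents as well as outcomes, a non-AE incident can keep its own 5-working-day deadline while the resulting symptom goes on the AE track. The gap is confined to UAPs that are themselves low-grade AEs.
- **That extrahepatic Y-90 on the research planar scan shows the reversal, reported promptly without symptoms and late with them.** If the finding counts as an abnormal sign under Section 6.6.2, it is an AE in both cases. If it does not, the displacement is a non-AE UAP in both cases. Neither reading gives a clear reversal. Since the protocol plans to look for it, it may not be unexpected either.
- **That new risks here will show themselves first as low-grade events.** The documents give no source for this. The remark in Section 7.2.1 that little is known in humans belongs to the efficacy sample size.

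Other points stand as limits. The class is narrow, because the common mild Optison reactions listed in Section 1.1 are expected and so would not ordinarily be UAPs. Quarterly DSMC reporting is a real, if partial, safeguard. Section 6.6.6 refers to Appendix C for the UAP definition, but the table available here shows none, so the UAP rules may be fuller than they appear. None of this supplies a stated IRB deadline for the affected events.

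**Conclusion.** The point holds for one defined class: risk-posing UAPs that are themselves non-serious Grade 1 or Grade 2 AEs. Followed as written, Section 6.6.6 reports them to the IRB later than risk-posing UAPs that are not AEs, and no sooner than UAPs without risk. This is the effect of a stated rule, not of missing detail.

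The 12-month, 7-to-8-patient and 23-session figures are ceilings. They assume annual review, even accrual, full attendance at three exams and an event just after a review. The IRB may set shorter intervals, and Section 3.1 allows missed visits. The conclusion also depends on the damaged Appendix C cell not holding a faster IRB route. Deadlines for Grade 3 to 5 events and serious events are a separate matter. This is a cheap improvement.

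**What to change.** In the UAP part of Section 6.6.6, delete the qualifier that restricts the 5-working-day sentence to UAPs that are not AEs. Any risk-posing UAP, whatever its grade, then goes to the IRB within 5 working days, or on the AE/SAE deadline if that is shorter. To the Grade 1 and Grade 2 lines add: *unless it is also a UAP that poses risk*. Check that Appendix C agrees with the revised text.

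The cost is two wording changes and a few more expedited IRB reports. Treatment, visits and analysis are unaffected.
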